9.1. Study design

This study will be a UK-wide, multi-centre, non-interventional cohort study (Figure 1). The study will involve secondary use of hospital medical records (paper-based or electronic, as

appropriate), collected both retrospectively and prospectively, from patients' medical records. Data will be collected for a maximum of 3 years following enrollment into the IPP.

[figure not shown]
Consent from living patients will be required if data are collected by pH Associates. In that case, patients will be provided with information about the study and approached for consent by members of the direct care team, either by post or in person at a routine hospital visit. Since no consent can be obtained if the patient is deceased, identifiable medical records of deceased patients will be accessed for study data collection by the direct care team only, to preserve confidentiality and avoid bias arising from exclusion of deceased patients.

Data will be collected retrospectively from the point of patient's enrollment into the IPP until initial data collection, expected to take place between November 2018 and February 2019. Members of the direct care team, or researchers from pH Associates (for living patients only), will collect existing (retrospective) data from the medical records of eligible patients in an electronic case report form (eCRF).

After the initial retrospective data collection, data will be collected prospectively up to a maximum of 3 years from enrollment in the IPP by members of the direct care team by updating the eCRF with any subsequent therapeutic and progression data available in the medical records until the end of the 3 year follow-up period.

The palbociclib initiation date will be defined as the index date. The baseline period will extend from the date of diagnosis up to palbociclib initiation (index date). The post-initiation observation period will be defined as the period from the index date until the end of the 3 year follow-up period. Patients will contribute data up to the time that they are lost to follow-up (for example due to discharge, death or other reasons) or 3-year post-index observation period, whichever is sooner.

Figure 1. Schematic of study design

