Definitions will be implemented as described in section 9.3 Variables. Patients who are known to be alive at the date of data collection (1-year for interim report and 3-year for full study report) will be censored at the date of data collection, and patients who are lost to follow-up will be censored on the date they were last known to be alive (e.g. date of last recorded hospital visit). Patients who are alive and free from disease progression at the date of data collection and those lost to follow-up will be censored on the date they were last known not to have disease progression (i.e. the date of last documented response assessment). Patients remaining in CR or PR at the end of the post-initiation observation period or lost to follow-up will be censored on the date CR or PR was last documented.

For the estimation of the proportion of patients alive, and free from disease progression, the denominator will be all patients known to be alive at the selected time-points (1 years, 2 years and 3 years). For the estimation of the proportion of patients achieving PR, CR and with stable disease at the selected time-points (1 years, 2 years and 3 years), the denominator will be all patients with at least one assessment of response (CR / PR / no response or stable disease / progressive disease) in the past year. Estimation of time to achieving best overall response and duration of response; and representation using swimmer plots will be performed in patients who respond (achieve CR or PR during follow-up) only.

Median PFS, OS, time to achieving best overall response, time to palbociclib dose modification and time to palbociclib discontinuation, and corresponding 95% CIs, will be estimated using Kaplan-Meier curves. Assessments of response (CR / PR / no response or stable disease / progressive disease) in patients responding to treatment (achieving CR or PR following initiation of palbociclib) will be represented using “swimmer plots”.

All percentages will be reported to the nearest whole number; therefore, in reporting study results in tables, figures and associated text, percentages may not add up to 100% due to rounding.

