9.9. Limitations of the research methods

- Comparisons of the results of this study with that of clinical trials and other real-world studies may be limited due to the presence of several potential sources of bias.
- Several sources of selection bias may be introduced in the study:

- At sites where data are collected by pH Associates, consent from living patients will be required; and consequently a low rate of consent amongst living patients may introduce an over-representation of deceased patients (for whom consent is not required) at those sites, and also compared to sites where consent is not required as all data are collected by the direct medical care team.
- Patients were treated as part of routine care and therefore patients enrolled in this study may have more diverse characteristics than in a clinical trial setting (for example with regard to menopausal status, ER and PR status, HER2 status), which may impact on the efficacy of palbociclib.
- Patients will be recruited from larger centres enrolled in the IPP, which may differ from smaller centres in terms of demographic and clinical characteristics, and therefore may not be representative of all patients treated with palbociclib in routine care as part of the IPP.
- Patients may be lost to follow-up due to the occurrence of AEs, lack of efficacy or other reasons, introducing attrition bias. However, the use of Kaplan-Meier curves will be used to obtain estimates of median PFS OS, CR, PR and this takes into account patient attrition.
- Radiological results will be collected from medical notes recorded by radiologists who were unblended to patient's treatment, introducing potential measurement bias.
- The interpretation of data collected retrospectively will be dependent on the completeness and quality of the medical records and the reliability of the abstraction of data from the medical records. However, SDV will be employed to identify and correct abstraction errors.
- This is a descriptive study and no analyses to control for confounding will be carried out; therefore, no definitive causal relationships between Ibrance® and study endpoints can be made.
- At sites where data are collected by pH Associates, a low consent rate may diminish sample size and the target of 250 patients enrolled into the study may not be achieved. If <200 patients are recruited into the study, an expansion of the study to other sites involved in the IPP will be considered.

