- Summary measures of bone profile in the first 6 months following initiation:
 - Calcium.
 - Phosphate.
- Summary measures of urea and electrolytes in the first 6 months following initiation:
 - Creatinine
 - Potassium
 - Sodium
 - Urea
- Summary measures of radiological indicators in the first 6 months following initiation including the proportion of patients with:
 - Stable disease.
 - Progressive disease.
 - CR or PR.

Secondary Objective 6: To describe BC-related healthcare resource utilisation during the first year following palbociclib initiation.

- Summary measures of hospital admissions for each line of therapy, including:
 - Proportion of patients with at least one inpatient admission recorded
 - Inpatient admissions per patient.
 - Elective or non-elective.
 - Reasons for admission (including day cases).
 - Length of stay per inpatient admission.
 - Proportion of patients with at least one outpatient visit recorded
 - Outpatient visits per patient.
 - Reason for outpatient visit
 - Type of HCP seen during outpatient visits
- Proportion of patients with at least one interaction with CNS
- Number of CNS interactions per patient
- Type of CNS interaction
- Reason for CNS interaction
- Proportion of patients with at least one interaction with AOS
- Number of AOS interactions per patient
- Type of AOS interaction
- Reason for AOS interaction

For the estimation of endpoints, *the following definitions will be implemented. PFS will be defined as the time from the date of palbociclib initiation to the date of first documented disease progression (as documented in the radiological assessment section of the eCRF) or death. OS will be defined as the time from the date of palbociclib initiation until death from any cause. Time to achieving best overall response will be defined in patients who respond to treatment as the time from the date of palbociclib initiation until*

PFIZER CONFIDENTIAL

achievement of the best overall response: CR, or PR if CR is not achieved during follow-up. Duration of response will be defined as the time from the date CR or PR was first documented (whichever is recorded first) to the date of first documented disease progression or death from any cause (whichever occurs first).

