8.2 STATISTICAL ANALYSES

Definitions will be implemented as in section 8.1.3. Patients who are known to be alive at the date of data collection (1-year for interim report and 3-year for full study report) will be censored at the date of data collection, and patients who are lost to follow-up will be censored on the date they were last known to be alive (e.g., date of last recorded hospital visit). Patients who are alive and free from disease progression at the date of data collection and those lost to follow-up will be censored on the date they were last known not to have disease progression (i.e., the date of last documented response assessment). Patients remaining in CR or PR at the end of the post-initiation observation period or lost to follow-up will be censored on the date CR or PR was last documented.

[figure not shown]
[figure not shown]
Note: Some analyses that were originally proposed were not conducted as per the decisions of the CI and Pfizer team, these have been kept in this section as a record.

8.2.1 Primary Objective: To describe patient demographic and clinical characteristics at initiation of palbociclib.

Proposed: Age, duration of MBC prior to palbociclib (calculated by subtracting the date of initial BC diagnosis from the date of palbociclib initiation), number of lymph nodes involved, tumour size at initial disease diagnosis and Ki67 values will be summarised as quantitative variables (see section 8.1.1) using measures of central tendency (mean and median) and dispersion (standard deviation, interquartile range [IQR] and range) will be calculated. All other variables analysed as part of the primary endpoint, whether categorical or binary, will be presented as frequencies and percentages.

Actual: Age was presented as both a quantitative variable as per section 8.1.1 and as a categorical variable (Categories: Less than 40 years old, between 40 and 50 years old,

PFIZER CONFIDENTIAL

[figure not shown]

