Describing treatment patterns 1,2 and 3 years after palbociclib initiation	Full Analysis set	Secondary Objective 1	Overall and Treatment Line	Frequency tables and percentages for proportions of patients completing a 28-day cycle, co-administered letrozole and fulvestrant at palbociclib initiation. Summary statistics calculated (incl. Mean/Median/SD/IQR/Range) for number of completed 28-day cycles	Excluded
Proportion of patients free from disease progression	Full Analysis set	Secondary Objective 2	Overall and Treatment Line	Frequency tables and percentages	Excluded
Proportion of patients alive	Full Analysis set	Secondary Objective 2	Overall and Treatment Line	Frequency tables and percentages	Excluded
Proportion of patients achieving PR/CR/with stable disease	Full Analysis set	Secondary Objective 2	Overall and Treatment Line	Frequency tables and percentages	Excluded
Median PFS	Full Analysis set	Secondary Objective 2	Overall and Treatment Line	Kaplan-Meier analysis, median PFS measured as being time from the date of palbociclib initiation to the date of first document disease progression or death. 95% confidence intervals calculated for median.	Standard imputation for dates (section 7), otherwise exclude.
Median OS	Full Analysis set	Secondary Objective 2	Overall and Treatment Line	Kaplan-Meier analysis, median OS measured as being time from the date of palbociclib initiation to the date of death. 95% confidence intervals calculated for median.	Standard imputation for dates (section 7), otherwise exclude.
Median time to best overall response (CR or PR)	Full Analysis set	Secondary Objective 2	Overall and Treatment Line	Kaplan-Meier analysis, time to first best overall response (partial/complete response) measured as being time from the date of palbociclib initiation to the date of first response. 95% confidence intervals calculated for median.	Standard imputation for dates (section 7), otherwise exclude.
Swimmer plots	Full Analysis set	Secondary Objective 2	Overall and Treatment Line	Swimmer plots used to represent patient response (CR / PR/ stable disease / progressive disease) to treatment for patients responding to treatment (CR or PR).	
Duration of response (PR/CR)	Patients enrolled achieving PR/CR	Secondary objective 2	Overall and Treatment Line	Kaplan-Meier analysis, median duration of response measured as being time from the	Standard imputation for dates (section 7),

PFIZER CONFIDENTIAL

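### The protocol credits Kaplan-Meier with handling attrition that may be outcome-related; PFS may be overstated to that extent, and no check is planned

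*Protocol*

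**What the plan says.** Protocol 9.9 lists attrition as a limitation: "Patients may be lost to follow-up due to the occurrence of AEs, lack of efficacy or other reasons, introducing attrition bias". The next sentence gives the mitigation: "the use of Kaplan-Meier curves will be used to obtain estimates of median PFS OS, CR, PR and this takes into account patient attrition".

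The PFS censoring rule is in Protocol 9.7 and is repeated in SAP 8.2. Patients alive and progression-free at data collection, and "those lost to follow-up will be censored on the date they were last known not to have disease progression", which both documents explain as the date of the last documented response assessment. The reason for loss plays no part. The preceding sentence in SAP 8.2, "patients who are lost to follow-up will be censored on the date they were last known to be alive", is the overall survival rule. Duration of response is treated like PFS: patients lost are censored when response was last documented.

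The PFS event differs between the documents. Protocol 9.3 accepts any mention of progression or mixed response in the medical records. SAP 6 takes first documented progression "as documented in the radiological assessment section of the eCRF) or death".

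The SAP 8.2.9 table has a single PFS analysis, overall and by treatment line, described thus: "Kaplan-Meier analysis, median PFS measured as being time from the date of palbociclib initiation to the date of first document disease progression or death". SAP 6 adds length of follow-up. Neither document states a non-informative censoring assumption, an alternative censoring rule or a tabulation of losses.

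**The concern.** Kaplan-Meier lets the patients still under observation stand in for those censored. That works only if the two groups have the same future risk. Loss for lack of efficacy is the usual example of where this fails: the patient leaves because the disease is worsening, and is censored at the last favourable scan. Section 9.9 names that mechanism as a possible cause of bias and then credits the estimator with a property it does not have.

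The SAP's narrower event definition adds to the risk. A patient with clinical worsening noted in the record, but no later scan, would be an event under Protocol 9.3 and censored under SAP 6.

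At stake is the reading of the clinical outcomes. Protocol 7 says the study may support assessments of the benefit of palbociclib in routine care, and a reader of 9.9 would think that attrition had been dealt with.

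**Working it through.** The documents give no loss rate, planned PFS or event count, so there is no stated figure to reproduce. What follows is illustration.

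**Inputs.** Median PFS 24.8 months, from the phase III first-line trial quoted in Protocol 7. Sample size about 250 (Protocol 9.5) or about 200 (SAP 2.1). Horizon 24 months (SAP 8.1). Assumed, not in the documents: exponential PFS, exponential loss of 5 to 30% by month 24, and a progression hazard after loss equal to k times the hazard before it.

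**Model.** λ = ln 2 / 24.8 = 0.02795 per month; μ = −ln(1 − loss)/24. Kaplan-Meier censors at loss and so estimates exp(−λt), with median 24.8, whatever k is. The true curve is

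S(t) = exp(−(λ+μ)t) + μ·exp(−kλt)·[1 − exp(−(λ+μ−kλ)t)] / (λ+μ−kλ).

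Example: 10% loss, k = 2, t = 24. μ = 0.00439, so S(24) = 0.460 + 0.037 = 0.497. Kaplan-Meier gives exp(−24λ) = 0.511, too high by 1.4 percentage points.

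**Kaplan-Meier minus truth**, as months in the median / percentage points in 24-month PFS:

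| Loss by month 24 | k = 0.5 | k = 1 | k = 2 | k = 4 |
|---|---|---|---|---|
| 5% | −0.4 / −0.5 | 0 / 0 | 0.5 / 0.7 | 1.0 / 1.5 |
| 10% | −0.8 / −1.0 | 0 / 0 | 1.0 / 1.4 | 2.0 / 3.0 |
| 20% | −1.7 / −2.0 | 0 / 0 | 1.9 / 2.9 | 3.7 / 6.0 |
| 30% | −2.7 / −3.1 | 0 / 0 | 2.8 / 4.4 | 5.1 / 9.1 |

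A simulation of 1,000,000 patients per cell agrees to about 0.1 month (for example, 3.6 months at 20% loss and k = 4).

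**Sampling error for comparison.** The 95% half-width of 24-month PFS, ignoring censoring, is 1.96·√(0.511 × 0.489 / n): 6.9 points for n = 200 and 6.2 for n = 250. For k = 2 to 4 the bias is 0.7 to 3.0 points at 5 to 10% loss, below the half-width. It exceeds the half-width only at 30% loss with k = 4.

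**Whether a median will be seen.** With true 24-month PFS of 51.1% and no loss, at least half the patients have an event by month 24 with binomial probability 0.40 (n = 200) or 0.38 (n = 250). On 2-year data, any bias would therefore show mainly in 24-month PFS.

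**The case against.** The strongest reply is that neither direction nor size is established. Section 9.9 says only that patients may be lost, and for several reasons. Loss through adverse events or discharge need not predict progression. The table shows no bias at k = 1 and understatement at k = 0.5. A reader might infer that PFS will be overstated, or that the protocol admits its censoring is informative; the text supports neither.

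This is also a record review. Stopping palbociclib is not a censoring rule, and later treatment lines, radiological assessments and deaths are still collected, so true loss may be small. That stands, although the SAP's radiological definition weakens the argument that lack of efficacy would already be recorded as an event.

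Section 9.9 also names a bias that may run the other way: low consent among living patients could over-represent the deceased. That arises at entry rather than through censoring, and cannot be assumed to cancel this one.

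A reader might use a starker calculation, in which a share q of progressions vanishes because patients leave just before them. The apparent median is then 24.8/(1 − q): 26.1, 27.6 and 31.0 months for q = 5%, 10% and 20%. That is an extreme bound and not an estimate, and those medians lie beyond the 2-year data. The 24.8 months itself comes from a first-line trial, whereas SAP 5.4 includes a second-or-later-line subgroup.

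Finally, PFS is a secondary endpoint in a descriptive study that already lists attrition as a limitation. This limits the weight of the point but does not make the stated remedy correct.

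**Conclusion.** The point holds in limited form. Section 9.9 attributes to Kaplan-Meier a protection that it gives only under non-informative censoring, immediately after naming a cause of loss that could violate that condition. PFS may be overstated to the extent that loss is related to impending progression. The same applies to duration of response if it is analysed: it is defined in SAP 6 and tabulated in 8.2.9, but is missing from the SAP 6 endpoint list.

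Under the assumptions above with k = 2 to 4, the median is overstated by about 1 to 2 months at 10% loss and about 2 to 3.7 months at 20%. At 5 to 10% loss the bias in 24-month PFS is below sampling error. These figures depend on an assumed loss rate, an assumed k and an exponential curve. The documents support no statement that bias will occur or of its net direction.

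**What to change.** 1. **Protocol 9.9.** Replace the claim with a statement that Kaplan-Meier estimates assume non-informative censoring and that loss related to lack of efficacy may bias PFS upward.
2. **SAP 8.2.** Add one bounding sensitivity analysis. Count patients lost to follow-up without documented progression as PFS events, at the censoring date or the last recorded visit; the SAP should name which. Exclude patients administratively censored at data cut-off, since the current rule treats both groups alike. Show the median, if reached, and Kaplan-Meier 24-month PFS beside the main estimate.
3. **Reporting.** Give the number and timing of losses. The listed dataset has patient status and last-visit date but no reason for loss. Unless the eCRF holds one, show the reasons for palbociclib discontinuation, which are already collected, in its place.
4. **Protocol 9.1 and SAP 2.1.** Clarify the text that lists death as an example of loss to follow-up, because death is a PFS and OS event.

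The cost is a few sentences, one extra Kaplan-Meier run and a small table from data already listed for collection. Abstracting a reason for loss would be new work and is not needed for the bound. The drawback is that the sensitivity estimate is a conservative bound: it will look less favourable and should be labelled as a bound.

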9.10. Other aspects

Not applicable.

10. PROTECTION OF HUMAN SUBJECTS

Not applicable

10.1. Patient Information

All parties will comply with all applicable laws, including laws regarding the implementation of organisational and technical measures to ensure protection of patient personal data. Such measures will include omitting patient names or other directly identifiable data in any reports, publications, or other disclosures, except where required by applicable laws.

The personal data will be stored at the study site in encrypted electronic form and will be password protected or secured in a locked room to ensure that only authorised study staff members have access. The study site will implement appropriate technical and organisational measures to ensure that the personal data can be recovered in the event of disaster. In the event of a potential personal data breach, the study site shall be responsible for determining whether a personal data breach has in fact occurred and, if so, providing breach notifications as required by law.

To protect the rights and freedoms of natural persons with regard to the processing of personal data, when study data are compiled for transfer to Pfizer and other authorized parties, patient names will be removed and will be replaced by a single, specific, numerical code, based on a numbering system defined by Pfizer. All other identifiable data transferred to Pfizer or other authorised parties will be identified by this single, patient-specific code. The investigator site will maintain a confidential list of patients who participated in the study, linking each patient's numerical code to his or her actual identity. In case of data transfer, Pfizer will maintain high standards of confidentiality and protection of patients' personal data consistent with the Clinical Study Agreement and applicable privacy laws.

